| 
 Referred to VAPOSH (at increased risk for post-operative complications) Abdominal surgery (upper GI, colorectal, hepatobiliary, pancreatic, intra-abdominal, | 
 Living in skilled nursing facility Having any surgery other than abdominal surgery A score of <21 (high school edu.) or <20 (less than high school edu.) on the Montreal Cognitive Assessment (MoCA) or Saint Louis |

| | |
|--|--|
| 
bladder, VATS/lobectomy and abdominal aortic aneurysm)
 
 • Age ≥ 60 years • Malnourished or at nutritional risk (PG-SGA and Nutrition Focused Physical Exam) • English speaking | 
University Mental Status (SLUMS) and inability to perform 1 or more activities of daily living (ADL).
 
 • A diagnosis of Galactosemia, a rare genetic metabolic disorder that affects an individual's ability to metabolize the sugar galactose properly. |
|--|--|

Only participants scheduled for a POSH clinic visit will be eligible for study participation. [name] or study staff will meet with the coordinator of the POSH clinic, weekly to identify eligible patients. We will screen and consent individuals until we meet the desired sample size of 84 subjects. The POSH clinic has over 300 visits annually.

To protect vulnerable populations or those subjects who may be susceptible to coercion or undue influence against, any Veteran who is approached by staff will be told that their participation is voluntary, and they may choose not to answer any questions that they find too sensitive. Also, Veterans will be told that their participation will not affect their care at the VA. The study staff member will explain the study in detail. No study procedures will begin until formal, written informed consent has been obtained.

Subject Recruitment

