This study will utilize a Request for HIPPA waiver of Authorization and waiver or alteration of informed consent process to identify potential participants for this research study. This study will be conducted in the context of the POSH clinic and will only include patients who participate in the POSH clinic. Identification of POSH patients: patients scheduled to be seen in general surgery clinic will be screened for candidacy for a POSH referral through CPRS. Specific referral criteria are based on established risk factors for post-operative complications and include age ≥ 60 , multiple comorbid conditions, falls, mobility limitation or documented functional impairment. In addition to an alert being sent to the surgical team, a notice will be sent to the PCP, with information about the program and an invitation to contact the program manager with any questions or additional information. Patients will receive a single appointment to see the POSH team.

Once patients are referred to the POSH clinic, the POSH clinic coordinator, will contact the study staff. At that time, a chart review will be conducted to assess initial eligibility (abdominal surgery, surgery date is at least two weeks after to POSH clinic visit). Potential participants identified will then be sent an introductory letter signed by the PI that describes the study and informs them that they will be called regarding participation. In the letter, potential participants will be given an "opt-out" number to call in order to decline participation and/or further contact regarding participation. Five business days after the mailing, Veterans who have not called the study number to decline participation will be called by a study staff member to request their participation in the research study (see telephone screen script). In the telephone contact, the study staff member will inform the Veteran that he/she was selected for recruitment because he/she is an older Veteran who is been seen at the POSH Clinic and is having abdominal surgery and may be at nutritional risk.

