Any Veteran who contacts or is contacted by study staff will be told that their participation is voluntary, and they may choose not to answer any questions that they find too sensitive. Also, Veterans will be told that their participation will not affect their care at the VA. The study staff member will explain the study in detail, including compensation. No study procedures will begin until formal, written informed consent has been obtained.

Consent Process

On the day of their POSH clinic visit, potential participants identified we will be informed again that he or she is being recruited because he/she is having abdominal elective surgery and is a patient in the POSH clinic. The participant will be told that their participation is voluntary, and they may choose not to answer any questions that they find too sensitive. Also, Veterans will be told that their participation will not affect their care at the VA. The study staff member will explain the study in detail. The participant will be given as long as they need to read through the consent form and HIPAA Authorization. Study staff will answer all questions and concerns. No study procedures will begin until formal, written informed consent has been obtained.

Study Interventions

Caloric Intake and Monitoring Protocol for Both Arms: Caloric needs will be prescribed for each participant using an established standard of 30 to 35 kcal/kg⁴¹ at the VAPOSH clinic. To assure adequacy for all enrollees, calculated protein needs will be higher than the recommended 0.8 g/kg of body weight for both arms, **PoshControl** protein prescription = **1.0 g/kg of bodyweight** and **PeriHab** protein prescription = **1.6 g/kg of bodyweight**. Participants will be monitored by weekly phone calls during which study staff will ask the participant to recall their intake from the day before (24-hour dietary recall). This information will be used to ensure that both arms are meeting their calorie needs. If a participant in either arm has an inadequate intake they will be counseled on how to increase their current intake. Based on our previous assessment of similar populations, it is unlikely that the **PeriHab** arm will be able to meet the 1.6 g/kg of body weight protein prescription on their own and for that reason we are providing protein supplement to be consumed 3 times a day (as described below). The **PoshControl** arm will be given one ONS to consume every day prior to surgery.

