Data management and quality control: We will employ REDCap (Research Electronic Data Capture) for data entry. Key components of this activity include data entry screen programming and database testing and validation. The database will include study default parameters and ranges for database, protocols, users, and access rights. Access and data entry to the database will be controlled by login permissions, and the database will be backed up daily, with full backups occurring weekly, and quarterly backups retained for perpetuity. The database will be routinely checked for data integrity and quality. In addition, since some data will require direct download from computerized databases (e.g. VA patient information, lab findings) a final relational database will be built to be used for analysis in SAS, combining data from all data sources. This process will include quality control, developing an appropriate query, validation, and justification procedures, auditing, developing a manual of procedures and documentation, interim reporting of data flow, and maintaining security and patient confidentiality of the data base. The analysis database derived from this source data will be de-identified. Identifying information will be viewed and managed only by the data manager and appropriately consented data collection staff.

Quality control procedures will be established for each component of the study. At each level of data management, and for each subject contact, strict adherence to VHA policy will be observed regarding HIPAA, IRB and other VHA patient quality controls. These procedures include not identifying any patient or provider on any of the reports generated from this study. All computer files will be password protected. Files containing names and addresses will have a separate password, will be accessible only to personnel who need to contact the subjects, and will be stored separately. Ultimately, a de-identified file appropriate for analysis will be produced for report generation and analysis. All analysis and Data management personnel are current with all VA mandated security training.

Aim 2.1 Analysis Plan:

Feasibility proportions for future screening and recruitment will be calculated at the end of the intervention using the following:

1. Proportion of patients recruited will be calculated as the number of patients deemed potentially eligible and contacted for enrollment divided by the total number of patients enrolled.

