 - Feasibility Hypothesis: $\geq 75\%$ of patients approached for recruitment will agree to participate

Fidelity proportions will be calculated for adherence and retention at the end of the intervention using the following:

1. Proportion adherent to nutrition intervention will be computed by the number of empty supplement containers divided by the number of possible supplement containers that could be consumed.

2. Proportion adherent to nutrition intervention will also be computed by the number of meals consumed that are 25 grams of protein divided by the number of possible meals that could be achieved. For the PoshControl arm, adherence will be assessed by the number of dietary changes they make based on the educational handout provided to them at baseline. These will be determined by using diet records for 3 days prior to surgery and 3 days following surgery. Diet food records are valid method for collecting dietary intake data and have been administered in Veteran populations.⁴² We have experience administering and analyzing this data.¹

- Adherence Hypothesis: $\geq 75\%$ of the time PeriHab participants will adhere to the intervention and $\geq 75\%$ of the time controls will show at least one recommended dietary change in their 3-day diet record

3. Proportion retention will be computed by dividing the number of retained subjects at the end of the intervention by the total number randomized into the study.

- Retention Hypothesis: $\geq 80\%$ of participants will remain in the study for the duration of the trial

We will calculate these rates of retention and adherence and their respective confidence intervals overall and by group. While non-powerful, we will assess if these rates differ by chi-square test of proportion and Poisson regression respectively. In a series of sensitivity tests, we will assess if adherence overall was impacted by demographic or symptomatic variables (such as chronic health conditions, living arrangements, surgery, functional status, and nutrition status).

Acceptability will be assessed by:

1. Calculating levels of attrition.

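### The recruitment proportion does not say whether Veterans who opt out after the letter count as approached; if only those telephoned count, the agreement rate is too high

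*Combined protocol and SAP*

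**What the plan says.** In the Aim 2.1 Analysis Plan, the first feasibility item defines the proportion recruited as the "number of patients deemed potentially eligible and contacted for enrollment divided by the total number of patients enrolled". The hypothesis beneath it is that at least 75% "of patients approached for recruitment will agree to participate". The same target appears under Specific Aim 1.1.

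Subject Recruitment sets the order of events. A chart review assesses initial eligibility. After that, "Potential participants identified will then be sent an introductory letter signed by the PI". The letter gives a "number to call in order to decline participation and/or further contact regarding participation". Five business days after mailing, "Veterans who have not called the study number to decline participation will be called by a study staff member to request their participation".

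No section defines *contacted for enrollment* or *approached*, or says how a Veteran who uses the opt-out number is counted.

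**The concern.** A Veteran who uses the opt-out number may be refusing participation, and has already been judged potentially eligible on chart review. By design that Veteran never gets the recruitment call. If the proportion rests on Veterans telephoned, it is conditional on not having refused already, and the earliest refusals vanish from it.

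The plan says that these proportions serve future screening and recruitment. A rate among those called would understate how many clinic patients the larger trial must approach per participant. There is also a problem of pre-specification: one analyst could count letters and another calls, and both would comply with the text. The choice could be made once the opt-out count is known, and it can decide whether the 75% target is met.

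**Working it through.** **Which contact is meant?**

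- For the telephone call: the call is where participation is requested. Subject Recruitment itself names it a telephone contact, and later says "Any Veteran who contacts or is contacted by study staff will be told that their participation is voluntary", with the study then explained in detail. That describes a conversation.
- For the letter: it goes to the potentially eligible, and its opt-out covers *further* contact, which implies that the letter is already a contact.

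The call is the likelier meaning, but the text does not settle it.

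**Formulas.** Let E be the number enrolled, C the number called, K the number of opt-outs, and o = K/(C + K) the opt-out share.

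- As written: contacted/enrolled = C/E.
- Turned over, calls only: E/C.
- Turned over, all approached: E/(C + K) = (E/C)(1 − o).

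The calls-only rate therefore exceeds the rate among all approached by the factor 1/(1 − o).

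**Inputs.** The 75% target is a threshold set in advance, so there is no calculated figure to reproduce. For illustration E = 84, the planned sample size under Selection of Subjects ("We will screen and consent individuals until we meet the desired sample size of 84 subjects"). Then C = 84/0.75 = 112 gives exactly 75% among those called. For simplicity, everyone called is taken as reached and eligible, and everyone who agrees as enrolled. The opt-out shares are assumptions.

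| Assumed o | Mailed = 112/(1 − o) | Enrolled/mailed = 0.75(1 − o) | Agreement among called needed for 75% of mailed = 0.75/(1 − o) |
|---|---|---|---|
| 0% | 112 | 75.0% | 75.0% |
| 5% | 117.9 | 71.3% | 78.9% |
| 10% | 124.4 | 67.5% | 83.3% |
| 20% | 140 | 60.0% | 93.8% |
| 30% | 160 | 52.5% | not attainable |

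At o = 25% the last column reaches 100%; above that, 75% of all mailed cannot be reached.

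**The formula as written.** C/E = 112/84 = 1.33. It cannot fall below 1 if everyone enrolled was contacted, so it cannot be compared with 75%. In that form, leaving out opt-outs lowers the figure: 1.33, against 124.4/84 = 1.48 at 10% opt-out. The upward bias exists only once the ratio is turned over, which the target requires.

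**Away from the threshold.** With 85% agreement among those called and 10% opting out, 0.85 × 0.90 = 76.5%. With 80% and 5%, 0.80 × 0.95 = 76%. Both still meet the target.

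**The case against.** The strongest reply is that the exclusion is inferred. If the letter is the contact, opt-outs are already in the count and there is no bias. If instead *approached* means an approach in person, a denominator of Veterans whom staff spoke to matches the hypothesis. Selection of Subjects uses the word for an approach by staff, and Specific Aim 1.1 speaks of recruitment in clinic. A mismatch between target and formula arises only if *approached* includes the letter and *contacted* does not. It can also be said that the definite error in this sentence is the inversion, and that its repair must name a denominator anyway.

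Much of this stands. A reader might infer that the plan excludes opt-outs and so overstates agreement; the documents do not support that as a stated rule. A reader might also infer that any opt-out at all turns a pass into a miss; that is true only when agreement among those called is exactly 75%. Nor do the documents show that Veterans who could not be reached are left out: all who have not opted out are to be called, and whether an unanswered call is a contact is unspecified. Counting every unreached letter recipient as a refusal would measure overall yield rather than agreement, and the plan does not require it.

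What the reply does not remove is the gap. Turning the ratio over does not say who belongs in the denominator, and the two readings can give different answers against the target.

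**Conclusion.** The concern holds as an undefined denominator with a conditional bias. It is established that opt-outs never receive the recruitment call and that the plan does not say how to count them. If *contacted* means telephoned and the ratio is corrected, agreement is overstated by 1/(1 − opt-out share). The direction follows from arithmetic. The size rests entirely on assumed opt-out shares, and whether the conclusion against 75% would change cannot be known from the documents. Because feasibility is a stated purpose of the pilot and the repair is small, the change should be made.

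**What to change.** In the sentence that corrects the ratio, define the proportion as those enrolled (or agreeing) divided by those approached. State that potentially eligible Veterans who opt out after the letter count in the denominator as approached and declined.

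Report the cascade: mailed, opted out, reached, agreed, consented. Show unreached Veterans and those found ineligible at telephone screening separately, not as refusals. The rate among those reached by telephone may be given as a secondary figure.

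The cost is one sentence and a short table. Opt-out calls already come to the study number, and staff need a record of them to avoid calling those Veterans. The downside is a somewhat less favourable rate. Some opt-outs might also have proved ineligible at telephone screening; the cascade lets a reader judge how much that matters.

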Setting: The POSH Clinic is an interdisciplinary collaboration between surgery, anesthesiology, geriatrics, nursing, and physical therapy to provide perioperative surgical care for high-risk Veterans at the Durham VAMC. The clinic opens with a conference to review patients to be seen that day. The surgery chief resident presents and the team covers technical issues with the surgery and selection of anesthesia, as well as covering a list of specific care points. The POSH clinic estimates 200 – 400 patients enrolled annually.

VAPOSH Veterans who are malnourished or at risk of being malnourished will be randomly assigned on a 1:1 ratio by computer-generated random numbers to either an education (nutritional counseling) control (PoshControl) arm or high-protein perihabilitation (PeriHab) arm. All will receive nutrition education. Participants in the PeriHab arm will also be provided with high quality protein supplements that will bring their protein intakes to at least 30 grams for each of the 3 meals per day.

Study Arms:

- PoshControl; n = 42: During their VAPOSH clinic visit, participants will be provided nutrition counseling and prescribed to consume protein at 1.0 g/kg of body weight in the form of educational handouts explained by a Registered Dietitian. Participants will also be instructed to consume 1 oral nutrition supplement per day two weeks before surgery.
- PeriHab; n = 42: PeriHab will be provided nutrition counseling and prescribed to consume protein at 1.6 g/kg of body weight) as well as provided 30 g of high quality protein to some 3 times per day for 2 weeks before and 4 weeks after surgery.

Measurements:

After the participant has been consented and HIPAA Authorization forms have been signed, a Registered Dietitian will administer the NRS-2002 screening tool, the PG-SGA, and nutrition focused physical exam. A patient screening “nourished” on the NRS-2002, PG-SGA, and nutrition focused physical exam will not be included in the study. For study candidates who are malnourished or at nutritional risk we will then proceed with baseline assessments (described below). Upon the completion of all baseline assessments, the participant will be randomized to PeriHab or PoshControl. The following variables will be blocked in this order: 1) surgery type and 2) American Society of Anesthesiology (ASA) Physical Status Classification System (≥ 3 versus < 3). An equal number of participants will be randomized across the two arms.

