PeriHab Arm Protein Perihabilitation Protocol: The protein supplementation protocol provides for three daily supplements of 30 g of high quality protein in the form of a liquid nutritional supplement (30 g). Subjects will receive sample menus to help the participants incorporate the increased protein into their daily intake. Individually packaged portions of the liquid supplement will be supplied at the VAPOSH clinic visit (T1). Participants will be given a two-week supply of supplement. Included will be a printed check-off sheet for participants to record protein supplement use. The protein check-off sheet, three-day food record, Actigraph log, and lids from the protein drink will be turned in on the day of surgery (T2). Following their surgery, participants will be given an additional four week supply of the same supplement at discharge and the same materials as at the VAPOSH clinic visit (T1). The protein check-off sheet, three-day food record, Actigraph log, and lids from the protein bottles will be turned in at the follow-up appointment (T3).

Participants will be contacted weekly by study staff and queried with a standard set of open-ended questions designed to identify problems with compliance. Participants who are having difficulty will be provided additional counseling to ensure they are able to achieve 30 grams of high quality protein three times a day.

PoshControl Arm Protocol: Participants in the PeriControl arm will be asked to consume 1 ONS protein supplement per day prior to surgery. They will be provided education on the role of nutrition to prepare for and heal from surgery with the following main messages, 1) complications associated with malnutrition; 2) the benefits of good nutrition; 3) tips for dietary intake when not hungry; 4) easy food preparation; and 5) what to eat. The study Registered Dietitian will instruct the participant to follow the information on the handout. Study staff will call the PoshControl arm participants once a week to identify problems with compliance,

answer any questions and also remind participant to complete their 3-day food records. The ONS check-off sheet, three-day food record, and lids from the Ensure Plus bottles will be turned in on the day of surgery (T2). Four weeks following surgery, PoshControl participants will return for a follow-up appointment and will bring Ensure Plus checklist, three-day food record, and Actigraph log.

Adverse Events

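### Container adherence runs before and after surgery in PeriHab but only before surgery in PoshControl, so comparing or pooling it across arms would confound arm with period

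*Combined protocol and SAP*

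**What the plan says.** **The measure.** Item 1 of the fidelity list in the Aim 2.1 Analysis Plan computes adherence as the "number of empty supplement containers divided by the number of possible supplement containers that could be consumed". It names neither an arm nor a period. After the list the plan states: "We will calculate these rates of retention and adherence and their respective confidence intervals overall and by group". Differences between arms are then to be tested, by Poisson regression in the case of adherence. No offset, stratum or period restriction is mentioned.

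**A second measure.** Item 2 adds a meal-protein measure and says that PoshControl adherence will be judged by dietary changes, using diet records from three days before and three days after surgery. The 75% hypothesis for controls is set on dietary change, not on containers.

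**PeriHab supply.** Study Arms gives the supplement "3 times per day for 2 weeks before and 4 weeks after surgery". The PeriHab protocol under Study Interventions specifies "three daily supplements of 30 g of high quality protein". At the clinic visit (T1), "Participants will be given a two-week supply of supplement"; after surgery, "participants will be given an additional four week supply of the same supplement at discharge". Lids are returned on the day of surgery (T2) and again at follow-up (T3). The approach text under Specific Aim 1.2, read literally, gives two weeks on each side of surgery instead.

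**PoshControl supply.** Study Arms, the caloric-intake paragraph and the PoshControl protocol all describe one supplement a day before surgery. The last of these says that "lids from the Ensure Plus bottles will be turned in on the day of surgery (T2"). At T3 these participants bring a checklist, but no lids are listed.

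**The concern.** The same ratio covers different stretches of time in the two arms. Only PeriHab is observed after abdominal surgery, when intake may well fall. If it does, PeriHab will show lower container adherence than PoshControl even when both arms behaved identically over the two weeks they share. A container rate pooled over both arms carries the same imbalance, and is also dominated by PeriHab because that arm has far more containers.

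The trial exists to show whether a regimen given before and after surgery can be followed, and to inform a larger trial. A lower PeriHab rate could be read as showing that three supplements a day are harder to sustain than one, when part or all of the gap came from the post-operative weeks.

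**Working it through.** The plan states no precision or power figure for adherence. Its one power figure, a detectable standardized difference of 0.634 with 40 per group, concerns physical function. It reproduces (0.6343 from the two-sample t test, 78 df) but has no bearing here.

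**Possible containers per participant** (days × containers per day, from Study Arms and Study Interventions)
- PeriHab before surgery: 14 × 3 = 42. After surgery: 28 × 3 = 84. Total 126.
- PoshControl before surgery: 14 × 1 = 14. After surgery: 0.
- Post-operative share in PeriHab: 84/126 = 66.7%.

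**How firm is that share?** The post-operative supply starts at discharge, while the Specific Aim 1.2 text puts the last assessment four weeks after surgery. If containers count only from discharge, the share is (28 − L)/(42 − L) for a stay of L days. Assumed stays of 3, 5 and 7 days give 64%, 62% and 60%. The Aim 1.2 text read literally gives 14/28 = 50%.

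**Effect on a container comparison.** PeriHab rate = (42 × pre + 84 × post)/126; PoshControl rate = pre. All adherence levels are assumptions, with the pre-operative level equal in both arms.

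| Before surgery, both arms | PeriHab after surgery | PeriHab rate | PoshControl rate | Gap (points) |
|---|---|---|---|---|
| 90% | 65% | (37.8 + 54.6)/126 = 73.3% | 90% | 16.7 |
| 85% | 75% | (35.7 + 63.0)/126 = 78.3% | 85% | 6.7 |
| 85% | 85% | 85% | 85% | 0 |

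For the first row, counting from discharge gives gaps of 16.0, 15.5 and 15.0 points for stays of 3, 5 and 7 days. The literal Aim 1.2 schedule gives 90 − (0.90 × 14 + 0.65 × 14)/28 = 90 − 77.5 = 12.5 points.

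**A real arm difference can be hidden.** With 90% v 75% before surgery in favour of PeriHab and 60% after surgery, PeriHab scores (37.8 + 50.4)/126 = 70%. A true advantage of 15 points over the shared period appears as a deficit of 5.

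**Chance that a test flags the gap.** This uses a participant-level two-sample t test with 42 per arm, two-sided 0.05, and assumed between-participant SDs of 0.20, 0.25 and 0.30. A 16.7-point gap is significant 97%, 86% and 71% of the time; a 6.7-point gap, 33%, 23% and 17%. This is not the planned Poisson model, so it indicates scale only.

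**Pooled rate.** Summing containers over 42 participants per arm gives 42 × 126 = 5292 from PeriHab and 42 × 14 = 588 from PoshControl. PeriHab supplies 5292/5880 = 90% of the pool, and its post-operative containers alone supply 3528/5880 = 60%. Restricting to T1–T2 removes the period imbalance but leaves PeriHab at 42/56 = 75% of containers, so participant-level proportions are still needed.

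**The case against.** **The plan may not compare containers at all.** It assigns PoshControl a dietary-change measure and never says that the compared or pooled rate is the container ratio. This stands, and it makes the concern conditional. It does not remove it: item 1 names no arm, item 2 is worded as an addition to item 1, and PoshControl lids are collected although no other planned analysis counts containers. If only dietary change is meant for controls, the arms would be compared on different measures, which is a separate problem. The diet-record windows fall on both sides of surgery, so the period imbalance is specific to containers.

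**The period effect is assumed.** This also stands. The documents give no adherence by period, and the contribution is zero if PeriHab adherence does not change after surgery. The plan itself concedes that the comparison has little power, and attaches no decision to it.

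**The 75% PeriHab target.** A reader might infer that one six-week figure misweights this target and that each period should have to reach 75%. The documents do not support that. The hypothesis concerns adherence to the intervention, and on the Study Arms schedule the 1:2 weighting is the regimen's own composition. A rule for each period would be a new success criterion. Period-specific rates are still informative: 45% before and 90% after surgery gives (18.9 + 75.6)/126 = 75%, a pass that the single figure could not explain.

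**Conclusion.** The point holds in conditional form. If the container ratio is compared or pooled across arms as item 1 allows, arm is confounded with period, because about 60–67% of PeriHab's possible containers are post-operative (50% on the literal Aim 1.2 wording) and none of PoshControl's are. The resulting gap is about 17 points under an assumed fall from 90% to 65%, about 7 points under a fall from 85% to 75%, and nil without a fall.

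A reader might go further and conclude that the comparison would measure the period and not the arm. That is too strong. The comparison mixes the two: with 75% v 90% before surgery and PeriHab unchanged at 75% afterwards, the whole 15-point deficit is an arm difference. The plan is also ambiguous about which measure is compared. This is a cheap improvement to a secondary fidelity analysis; it does not undermine the trial.

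**What to change.** In the fidelity section of the Aim 2.1 Analysis Plan:

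- State which adherence measure is compared, and which is pooled, in each arm.
- Compute container adherence separately for T1–T2 and T2–T3.
- Make any between-arm or pooled container analysis on T1–T2 only, using participant-level proportions or a Poisson model with an offset for possible containers, so that the 3:1 container volume does not drive the result.
- Report PeriHab T2–T3 adherence as a single-arm estimate with its confidence interval.
- Keep the 75% PeriHab hypothesis on the whole regimen, and show the period-specific rates beside it as description.

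The statements of the PeriHab supplement period under Specific Aim 1.2, Study Arms and the PeriHab protocol must be reconciled, including the start of post-operative supply at discharge, because they set the denominator.

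The cost is wording and one extra table. Lids are already returned separately at T2 and T3, so no new data are needed. The downside is slightly wider intervals for the period-specific rates.
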